## 1.0 Objectives

### 1.1 Study Objectives

Using a randomized double-blinded study design, our goal is to evaluate the superiority of Erector Spinae Plane block (ESPB) in the peri-operative pain management in patients undergoing surgery through flank or anterior subcostal incisions as compared to the standard of care of using IV and oral opiates.

### 1.2 Primary Study Endpoints

1. Pain scores using the Visual analogue scale (VAS) 0-10 on postoperative day 1. (VAS scale document attached)

### 1.3 Secondary Study Endpoints

1. Pain scores using the Visual analogue scale (VAS) 0-10 on postoperative day (POD) 2 and 3.
2. Total dose of IV and oral opiate and study drug use at the completion of POD 1, 2 and 3.
3. Length of hospital stay
4. Patient satisfaction survey of pain control given on POD 1, at discharge and at time of postoperative visit (within 14 days of discharge)—(survey document attached)
5. Amount of oral opiates used from discharge to postoperative visit
6. Total cost of hospital stay

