#### 7.2.3 Day of Surgery - Pre-op

**In the SDU**, [name] will be present to ensure the current surgery and anesthesia team for the study patient are sufficiently educated on the protocol requirements and to ensure safety and protocol adherence. The patient will receive a study bracelet with the study ID and patient's specific randomization ID. The block procedure will be performed in the SDU by a member of the anesthesia block team, who is also part of the research team. The placement of the erector spinae catheter will occur according to standard practice guidelines using strict sterile conditions and is similar regardless of type of study medication that the patient will be randomly receiving. After the block catheter is placed, a member of the research team will pick up the study drug from the pharmacy, deliver it to the SDU and ensure the correct coordination of study drug to the patient using the patient's study ID bracelet. The ESP catheters will be bolused with 20 ml of Ropivacaine 0.5% vs 20ml of normal saline (placebo). Following this initial bolus, the ESP catheter will be connected to a pump containing Ropivacaine 0.2% or normal saline which will

deliver automatic boluses of 15ml of either study medication or normal saline every 3 hours. The automatic bolus dosing of 0.2% Ropivacaine is based on the standard dosing for all adults weighing between 50-120kg.

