#### **7.2.5 Postoperative hospital stay**

As per standard of care, the patient will be taken to the post anesthesia care unit (PACU). Here, [name] will be present to ensure the PACU team for the study patient are sufficiently educated on the protocol requirements and to ensure safety and protocol adherence. The ESPB pump will be delivering the automatic boluses of study drug (15ml every 3 hours) and additionally allow the patient to self-administer an on demand dose of study drug (0.2% Ropivacaine vs. normal saline) 5ml every 30 minutes throughout their hospital stay. The pump will permanently lock out and cease administration of both the automatic and self-administered boluses if the total dose of study drug reaches 770mg. The patient will still be able to initiate a demand dose, but no medication will be provided. If a lock out occurs prior to POD3, when the pump is scheduled to be removed, it will remain in place until the schedule day of removal. In the PACU, if the patient has additional pain requirements beyond the patient's previously determined acceptable pain score (asked pre-operatively per hospital standard) the PACU team may start a patient controlled analgesia (PCA) containing a set demand dose of hydromorphone 0.2mg every 6 mins. The pump will lock out if the maximum dose of 2mg per hour is reached. Bolus IV dosing of hydromorphone may be administered at the start of the PCA and throughout the hospital stay if deemed necessary by the treating physician team to control patient pain needs. One gram of acetaminophen IV every 8hrs will also be started in the PACU and continued through the patient's hospital stay. Acetaminophen will be converted over to oral regimen on POD 1. When transferred to the inpatient wards, [name] will ensure the nurse assigned to the study patient is aware and properly educated on the protocol requirements on a daily basis. She will also monitor for subject safety and protocol adherence while the study patient remains in the hospital by both identifying the patient room as on a research study as well as through daily interaction with the nursing team. While on the inpatient wards, additional pain control adjuncts will be provided using oral oxycodone 5-10mg every 4 hours administered based on a pain scale: pain 3-6 translates to 5mg tab and pain 7-10 translates to a 10mg tab. The PCA, as outlined above, may be started later in the hospital course, if needed, based on the patient's needs. The ESP block will be discontinued between 6AM-9AM on POD 3. Specific research order sets for this study will be created by the principal investigator for use of the study drug/placebo, narcotics and acetaminophen. All medications and dosages administered during the hospital stay (PACU and inpatient ward) will be reviewed and documented by a member of the research team to tabulate the total IV and oral opioid and study drug requirement of all study patients. Daily pain scales using the Visual analogue scale (VAS) 0-10 will be provided to the patient by a member of the research team, each morning between 9AM-12PM, on POD 1, 2 and 3 (scale attached). Additionally, on POD 1, between 9AM-12PM, a brief patient satisfaction survey (which has been previously validated (11)) will be provided to the patient to complete by a member of the research team (document attached).

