### **7.4.6.3 Preparation and Dispensing**

Following randomization of study patients (randomization will occur the working day prior to scheduled operative date), the study drug will be packaged both in a syringe which will contain the initial bolus dose and also in a cartridge which will contain the automatic pump boluses. Both the syringe and cartridge which will be nonspecific to the medication type (Ropivacaine or Normal saline). The syringe and cartridge will be labeled both with the study ID and the patient's specific randomization number. The ESPB syringe and cartridge will contain Ropivacaine 0.2% and the SESPB syringe and cartridge will contain normal saline. All preparation, dispensing of drug into cartridges and cartridge labeling will occur by the investigational pharmacy, who will remain unblinded. The day of surgery, a member of the research team will pick up both the syringe and cartridge and deliver it to the SDU. Here, the syringe followed by the cartridge will be connected to the block catheters allowing administration to begin in the SDU.

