### **8.3 Statistical methods**

For the primary endpoint, a 2-sided t-test will be used. T-tests will also be used for all secondary endpoints, unless the assumption of normality does not hold, in which case a Wilcoxon Rank Sum Test will be used.

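### Secondary endpoint 2: by POD 3, and to a varying degree by POD 2, the study-drug total is set mainly by the fixed boluses and the 770 mg lock-out, so similar totals would not show similar patient demand

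*Combined protocol and SAP*

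**What the plan says.** Section 1.3, item 2 defines the endpoint as "Total dose of IV and oral opiate and study drug use at the completion of POD 1, 2 and 3". Section 8.3 gives the analysis: "T-tests will also be used for all secondary endpoints", with a Wilcoxon rank sum test if normality fails.

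Three delivery rules determine the study-drug part:

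- **Automatic doses.** The pump will "deliver automatic boluses of 15ml of either study medication or normal saline every 3 hours" (section 7.2.3), in both arms alike.
- **Demand doses.** From the PACU onward the patient may "self-administer an on demand dose of study drug (0.2% Ropivacaine vs. normal saline) 5ml every 30 minutes throughout their hospital stay" (section 7.2.5).
- **Lock-out.** The pump will permanently "cease administration of both the automatic and self-administered boluses if the total dose of study drug reaches 770mg" (section 7.2.5). After that, "The patient will still be able to initiate a demand dose, but no medication will be provided".

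The block is stopped between 06:00 and 09:00 on POD 3, so the total at completion of POD 3 is the total at removal.

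The loading bolus is described in two ways. Section 7.2.3 gives it at 0.5%: "The ESP catheters will be bolused with 20 ml of Ropivacaine 0.5% vs 20ml of normal saline (placebo"). Section 7.4.6.3 puts the syringe that holds it at 0.2%: "The ESPB syringe and cartridge will contain Ropivacaine 0.2"%. Neither section says whether it counts toward the 770 mg.

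**The concern.** The study-drug total has a programmed part that is identical by volume in both arms, a demand part that depends on the patient, and a ceiling that stops both. Only the demand part reflects how the patient feels. If the programmed part nearly fills the ceiling, the total is close to constant whatever the patient does, and presses after lock-out leave no trace in it.

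The risk is one of interpretation. A comparison at POD 3 that finds no difference could be reported as equal use of the pump, even if patients in one arm pressed twice as often as those in the other. Pump demand should separate a working block from a sham one, and the endpoint as defined discards much of that information at its later time points.

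**Working it through.** **The plan's own figures.** The plan gives no sample size or power for this endpoint. Its figure for the primary endpoint reproduces: a two-sided t-test at 0.05 with a difference of 2 and an SD of 2 needs 16.7, so 17 per group, with power 80.7%. Nothing below depends on it.

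**Inputs from the documents.** 0.2% is 2 mg/ml.

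- Automatic bolus: 15 × 2 = 30 mg every 3 h.
- Demand dose: 5 × 2 = 10 mg.
- Cap: 770 / 2 = 385 ml.
- Load: 20 ml × 5 mg/ml = 100 mg (section 7.2.3), or 20 ml × 2 mg/ml = 40 mg (section 7.4.6.3).

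**Assumptions not in the documents.** The pump starts between 06:00 and 13:00 on the day of surgery, the first automatic bolus comes 3 h later, and completion of a POD means midnight.

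**Formula.** Room for demand = 770 − counted load − 30 × floor(hours since start / 3), not below zero. Demand doses = room / 10.

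**07:00 start, at removal.** 06:00 on POD 3 is 71 h, so 23 boluses = 690 mg. 09:00 is 74 h, so 24 boluses = 720 mg.

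- Load not counted: 770 − 720 = 50 to 770 − 690 = 80 mg, or 5-8 doses.
- 40 mg counted: 10-40 mg, or 1-4 doses.
- 100 mg counted: 690 + 100 = 790, above 770, so none.

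**Starts from 06:00 to 13:00.** Room in mg, with demand doses in brackets:

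| Load | End of POD 1 | End of POD 2 | Removal on POD 3 |
|---|---|---|---|
| Not counted | 350-440 (35-44) | 110-200 (11-20) | 20-140 (2-14) |
| 40 mg counted | 310-400 (31-40) | 70-160 (7-16) | 0-100 (0-10) |
| 100 mg counted | 250-340 (25-34) | 10-100 (1-10) | 0-40 (0-4) |

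Without any demand, automatic boluses reach the cap at 69 h (100 mg counted), 75 h (40 mg counted) or 78 h (load not counted). Start to removal is about 65-75 h.

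**Two average patients.** Assume a 07:00 start, demand from hour 6, removal at 72.5 h, and request rates of 4 and 8 per day. Counting each request as one delivered dose until the cap:

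- End of POD 1 (41 h, 13 boluses = 390 mg): 35 × 4/24 = 5.8 and 35 × 8/24 = 11.7 requests. Totals are 390 + 58 = 448 and 390 + 117 = 507 mg, or 548 and 607 with the 100 mg load. The difference shows.
- End of POD 2 (65 h, 21 boluses = 630 mg): 59 × 4/24 = 9.8 and 59 × 8/24 = 19.7 requests. Load not counted: 630 + 98 = 728, and 630 + 197 = 827, cut to 770. With 100 mg counted: 828 and 927, both cut to 770.
- Removal (24 boluses = 720 mg): 66.5 × 4/24 = 11.1 and 66.5 × 8/24 = 22.2 requests. 720 + 111 = 831 and 720 + 222 = 942, both cut to 770 even without the load.

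**Simulation.** 20 per arm, Wilcoxon test, 08:00 start, demand from 5 h, and demand rates varying between patients with arm means of 0.25 vs 0.5, 0.25 vs 0.75 and 0.5 vs 1.0 doses per hour:

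| | End of POD 1 | End of POD 2 | POD 3 |
|---|---|---|---|
| At cap, 100 mg counted | 2-54% | 89-99% | 100% |
| Power, 100 mg counted | 69-98% | 9% or less | 0% |
| At cap, load not counted | 0-37% | 45-91% | 78-98% |
| Power, load not counted | 70-98% | 24-81% | 4-42% |

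A second simulation used 4 vs 8 and 8 vs 16 requests per day. With the load not counted, 4 vs 8 per day gave means of 11.0 vs 22.3 requests at removal but 382 vs 384 ml delivered. Power for the request count at POD 2 and removal was about 67-81% in every scenario. Power for POD 3 delivered volume was 25% and 5% with the load not counted, and 0% with either load counted. The rates are assumed, so these power figures only illustrate the pattern.

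**The case against.** The strongest reply is that the endpoint is read three times and has an opiate part. At the end of POD 1 there is ample room below the cap and a real difference in demand can appear. At POD 2 much depends on whether the load counts. The opiate part, which includes self-administered hydromorphone as well as oxycodone given by pain score, is untouched by the pump's cap and is the outcome closest to the opioid-sparing rationale in section 2.3. All of this stands. A reader might infer that the endpoint can show no difference at all, or that pump demand is the only self-titrated measure; the documents support neither.

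A reader might also infer that sham patients score 0 mg, which would make the test trivially significant. Section 7.2.5 describes the study drug in the pump as ropivacaine or saline, so the cap reads most naturally as a volume equivalent. The missing unit needs stating, but it is not evidence of a wrong test.

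The figures also rest on an undocumented start time and assumed request rates. Section 3.1 requires only a planned stay of 24 hours, so patients discharged early, and some of those withdrawn, would have lower totals. That weakens any claim that nearly every patient reaches the same total. Early departure would also move totals for reasons other than demand, so it does not make the POD 3 total a better measure of it.

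Finally, section 1.3 does not say that the total is meant to measure demand, and delivered volume is a legitimate record of exposure. That is a reason to report it as exposure, not to rest a between-arm comparison on it.

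**Conclusion.** The concern holds for the study-drug total at POD 3 and, to a degree that the plan leaves open, at POD 2. With a 07:00 start the room for demand over the whole stay is 5-8 doses, 1-4 doses or none, according to how the load is treated; across the assumed start times it is 0-14. Similar POD 3 totals would say little about demand.

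The POD 1 study-drug total, with 250-440 mg of room, stays informative, although patients with high demand can lock out before then. The opiate totals and the primary endpoint are unaffected. The headroom figures follow from the protocol's doses plus the assumed start time, first-bolus time and midnight cut-off. The simulated figures rest also on assumed demand. This is a worthwhile, inexpensive correction to one component of a secondary endpoint.

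**What to change.** In section 1.3, item 2:

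- Analyse opiate and study drug as separate variables.
- Express study drug in ml in both arms, split into automatic and demand volume.
- Base the between-arm study-drug comparison on patient demand: the number of requests, delivered plus undelivered and including those after lock-out, cumulative to the end of POD 1, the end of POD 2 and pump removal. The documents do not say whether the pump logs attempts, so confirm this first. If it does not, use delivered demand doses to the end of POD 1, where the cap binds least.
- Report total delivered volume as exposure only.

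Reconcile sections 7.2.3 and 7.4.6.3 on the concentration of the loading bolus, and state whether that bolus counts toward the 770 mg. No change to dosing or to the lock-out is proposed.

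The cost is a wording change, reading each pump's log at removal, and a skewed count, for which the Wilcoxon test already allowed in section 8.3 is suitable. The fallback loses the later time points and can still be cut short by the cap when demand is high.

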## 2.0 Background

### 2.1 Scientific Background and Gaps

Despite the advances in less invasive surgical techniques, the flank or anterior subcostal incision remains a widely used surgical approach for surgeries performed on upper urinary tract.(1) Post-operative pain control is a fundamental part of care for any patient undergoing surgery and is often challenging. These incisions, in particular, are known to lead to increased postoperative pain due to the multiple layers of abdominal musculature incised. It has been shown that inadequate peri-operative pain control can lead to chronic pain in postoperative patients.(2,3) Whereas, proper management of post-operative pain has shown benefits such as improved patient satisfaction, earlier mobilization, decreased length of hospital stay and even decreased hospital costs.(4,5,6)

Opioids are the most commonly used agents for peri-operative pain control. Despite being effective, opioid use is associated with a long list of side effects and its overuse may be a driver for chronic addiction. The use of neuro-axial techniques, especially epidural-analgesia, offered a successful alternative to opioid narcotic use. Yet, its use can be limited by coagulopathy, infection and anatomical abnormalities. Additionally, the use of an epidural, at times, can delay a patient's progress to hospital discharge. Thus, the need for developing alternative safe and effective opioid sparing pain management techniques has grown.

The goals of reducing postoperative narcotic requirements, in addition to the availability and high safety profile of the US-guided peripheral nerve block techniques, has provided a fertile landscape for studying new alternatives to epidural analgesia.(7) It is promising that the exploration of new techniques for perioperative pain management may improve patient satisfaction and outcomes through avoiding deleterious side effects, decreasing length of hospital stay and may overall decrease total costs.

## 2.2 Previous Data

Recently, the erector spinae plane block (ESPB) has been described in multiple case studies. In 2016, Mauricio and colleagues presented ESPB as a novel analgesic technique in thoracic neuropathic pain. The authors used the proposed block successfully to manage thoracic pain in 4 patients presenting with chronic thoracic pain (2 cases) and postoperative pain control following video assisted thoracoscopic procedures (2 cases). The same group has also utilized the same technique for postoperative pain control following ventral hernia repair and thoracotomy.

## 2.3 Study Rationale

Opioid analgesia is associated with multiple side effects and its overuse may be a driver of chronic addiction. Establishing opioid sparing techniques for perioperative pain control is crucial for providing effective and safe patient care after surgery.

# 3.0 Inclusion and Exclusion Criteria

## 3.1 Inclusion Criteria

1. Subjects undergoing open nephrectomy using a flank or anterior subcostal incision.
2. Consenting adults age 18-85
3. Patients weighing over 60 kg.
4. American Society of Anesthesiologists (ASA) Physical Status classification I to III
5. Planned to be hospitalized for at least 24 hours post-op
6. Cognitive capacity to use the visual analogic scale (VAS) and complete the patient satisfaction survey

## 3.2 Exclusion Criteria

1. Patient refusal
2. Patients with allergies to ropivacaine, local anesthetics, specifically amide anesthetics, or opiates (hydromorphone or oxycodone)
3. Scoliosis
4. Patients with chronic pain syndromes or who are on chronic pain medications/other neurologics of more than 3 months or whom have neuromodulators/stimulators
5. Concurrent surgeries requiring additional incisions on the body
6. Pregnant females (pregnancy testing included in study procedures)
7. Individuals with any clinically relevant history or the presence of neurological deficits or cardiovascular disease
8. Patients with a history of liver dysfunction

## 3.3 Early Withdrawal of Subjects

### 3.3.1 Criteria for removal from study

1. If the block cannot be placed/technically performed in the patient
2. If the subject does not follow protocol
3. If they are unable to participate cognitively after the surgery.
4. Any inpatient Clavian III or greater surgical complication
5. If surgery needs to be carried out via an incision other than flank or anterior subcostal
6. If the subject has an adverse event, such an allergic reaction attributed to the study drug, causing the patient to become unblinded
7. If the patient has pain requirements which exceed all options available in this protocol.

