### **3.3.2 Follow-up for withdrawn subjects**

If subjects need to be withdrawn from the study based on the above reasons, they will transition to following the clinical standard of care that is medically required for their particular situation. The block that is in place will be unblinded to the physician and patient. Unblinding will help the physician and patient understand if it may be worth trying to continue with the block in such circumstances as a means of pain control. Continuation with the blinding procedures could only delay achievement of adequate pain control and removal of unnecessary hardware, if the block ends up containing the control—normal saline. The remainder of the hospital course for these withdrawn subjects will continue according to standard medical practice. Their course will continue to be tracked for research purposes and they will be included and reported in the study results.

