### **12.0 Potential Benefits to Subjects and Others**

#### **12.1 Potential Benefits to Subjects**

Potential benefits of being a subject in the study include improved pain control, less nausea/vomiting, less sedation, fewer side effects from opiates, and decreased length of hospital stay.

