**19.6 Unblinding Procedures**

Unblinding of the study drug would occur if a patient developed an adverse reaction, such as an allergic reaction, attributed to the study drug. Documentation of the adverse reaction would ensue and the patient would be unblinded and then withdrawn from the study. Such a patient would then be cared for in context of standard medical practice and their remainder of their medical course would continue to be tracked for research purposes and reported in final study results. Additionally, in any instance that the subject is being withdrawn from the study, as listed in section 3.3.1, the subject will also be unblinded. Unblinding will help the physician and patient engage in a more meaningful and effective clinical interaction for pain control. There will be no confusion as to if the block may or may not contain active medication, Ropivacaine, and thus could be effective for the clinical scenario.

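### Two removal criteria have no threshold yet trigger unblinding, so later self-reported secondary outcomes of removed patients would be collected unblinded

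*Combined protocol and SAP*

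**What the plan says.** Section 3.3.1 lists seven criteria for removal. The second is "If the subject does not follow protocol" and the third is "If they are unable to participate cognitively after the surgery". Neither has a severity grade, a duration, a named assessor or a step for trying again. Nothing is said about return to the study.

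Two sections set out what follows. Section 3.3.2 moves the withdrawn subject to standard care and says "The block that is in place will be unblinded to the physician and patient". Section 19.6 applies this to every criterion: "in any instance that the subject is being withdrawn from the study, as listed in section 3.3.1, the subject will also be unblinded". Both give a pain-control reason: knowing what the catheter delivers helps physician and patient decide whether the block is worth using. Section 3.3.2 adds that staying blinded could delay relief and leave a purposeless catheter in place.

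On data, section 3.3.2 says "Their course will continue to be tracked for research purposes and they will be included and reported in the study results". Section 19.6 says much the same of a patient unblinded for an adverse reaction.

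The primary endpoint (section 1.2) is "Pain scores using the Visual analogue scale (VAS) 0-10 on postoperative day 1". The secondary endpoints (section 1.3) include the POD 2 and 3 VAS, opioid totals to POD 3 and after discharge, and satisfaction surveys on POD 1, at discharge and at the postoperative visit. Section 12.1 names as potential benefits "improved pain control, less nausea/vomiting, less sedation, fewer side effects from opiates". Section 8.2 raises 17 per group to 20 to cover withdrawals. Section 8.3 names no analysis set and no missing-data rule.

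**The concern.** A missed VAS and a lapse in adherence are events in data collection or conduct. The plan turns both into study withdrawal with unblinding, and unblinding cannot be undone even if the lapse is brief. VAS and satisfaction are rated by the patient, and opioid use depends on choices by patient and physician. Once both know the allocation and care has left the study regimen, these outcomes no longer measure the blinded comparison.

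For the cognitive criterion there is a plausible link to treatment. If the block reduces opioid use and sedation, as section 12.1 hopes, opioid-related impairment would be more common with saline, and so would removal for it. At stake is the blinded comparison on several secondary endpoints in a trial of 20 per arm and, in one narrow case, the primary.

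**Working it through.** **1. The plan's own figure.** Inputs from section 8.2: difference 2, SD 2, two-sided alpha 0.05, power 80%. The standardised difference is 2/2 = 1.0. The two-sample t-test (noncentral t) needs 16.71, so 17 per group, and power at 17 is 80.7%. The figure reproduces. The allowance is 20 − 17 = 3 per arm, or 3/20 = 15%. Power with all 20 per arm scored is 86.9%; with 20 and 17 it is 83.8%; with 16 and 16 it is 78.1%.

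**2. When the rule costs a primary score.** There are three cases.
- The patient cannot score at any time in the POD 1 window. The score is missing whether the patient is removed or retained, so the rule costs nothing here.
- Removal comes after the POD 1 VAS. The primary is intact.
- Removal comes before the POD 1 VAS, in a patient who could still have given a score that morning. The score is then either not taken or given unblinded. Only this case is due to the rule.

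**3. Size of the third case, under assumptions.** The documents give no loss rates by arm. The simulation used 40,000 trials, 20 per arm, normal scores, SD 2 and a true difference of 2.0, with 3 of 20 saline patients lost and loss tied to higher pain.

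| Assumed link of loss to pain | Estimated difference | Type I error if there is no true effect |
|---|---|---|
| correlation 0.3 | 1.84 | 5.8% |
| correlation 0.5 | 1.74 | 7.2% |
| three highest scores lost (extreme) | 1.48 | 14.8% |

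The same extreme loss in the active arm gives 2.51 instead of 2.0. The sign is therefore not known in advance, and a heavily sedated patient need not be one with a high pain score. A larger sample would not remove such a shift.

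**4. Secondary endpoints.** A patient removed on the morning of POD 1 has these items still to come: two VAS scores (POD 2 and 3), two surveys (discharge and telephone visit), and opioid use for the rest of the stay and after discharge. All would be unblinded, if collected. If *k* of 20 patients in one arm are affected and each report moves by *δ*, the arm mean moves by *kδ*/20. Taking *δ* = 2, the design difference, purely as a yardstick:
- *k* = 1: 1 × 2/20 = 0.10 points
- *k* = 2: 2 × 2/20 = 0.20 points
- *k* = 3: 3 × 2/20 = 0.30 points

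These are 5%, 10% and 15% of the 2-point difference.

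**5. Reason against criterion.** The pain-control reason in 3.3.2 and 19.6 fits the seventh criterion, where pain exceeds what the protocol can offer. A patient who cannot complete a scale, or who does not adhere, does not by that fact have uncontrolled pain. The documents give no other reason for unblinding these two groups.

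**6. What happens to the data.** Section 3.3.2 includes withdrawn subjects in the results, while section 8.2 adds patients as though withdrawals were lost. No section says whether the VAS continues after withdrawal or whether those scores enter the t-test.

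**The case against.** The strongest reply is that the cognitive criterion can be read as lasting loss of the capacity required by inclusion criterion 6, not as one drowsy morning. That reading is open. The text does not settle it, and this is why the criterion needs a definition.

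The reply also stands against four stronger readings that a reader might infer.
- *A temporarily drowsy patient is permanently removed and lost.* Section 3.3.1 says nothing on duration or return, and section 3.3.2 keeps withdrawn subjects tracked, included and reported. Length of stay, cost and recorded inpatient opioid use remain obtainable, though after unblinded care.
- *Dropping the criterion would save part of the three-patient allowance.* The allowance serves the POD 1 test, and a score missed through incapacity is missing either way. Only a successful second attempt recovers it, and nothing in section 7.2.5 forbids one.
- *Saline patients will be removed more often.* Section 12.1 lists potential benefits, not rates. For non-adherence, no link to arm is shown at all.
- *Any protocol deviation leads to removal.* The wording concerns the subject's own non-adherence, not staff deviations.

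Finally, section 3.3.2 ties unblinding to patient care, and the regimen includes patient-initiated demand doses (section 7.2.5). Cognitive inability may therefore bear on treatment as well as on scoring. That stands, so the remedy should be confined to data collection, blinding of assessments and analysis.

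**Conclusion.** The point holds for data and blinding. Two undefined criteria lead to unblinding for a reason that does not in itself apply to them, and the later self-reported outcomes of those patients would then be unblinded, with continued VAS collection unstated. The main harm is to the secondary endpoints: about 0.10 to 0.30 points on an arm mean if one to three of 20 patients are affected, assuming each report moves by 2 points. Both the number affected and the size of movement are assumptions.

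The primary is at risk only in the narrow case of removal before a POD 1 score that could still have been given. With three such losses in the saline arm, the estimate would fall from 2.0 to between 1.84 and 1.74 under a moderate assumed link with pain, or 1.48 at the extreme. A difference between arms is plausible for the cognitive criterion but not demonstrated. This should be changed, but it does not invalidate the primary analysis.

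**What to change.** State in section 3.3.1 that a missed VAS, or a protocol deviation by the subject, is not by itself study withdrawal and does not by itself trigger unblinding. Then:
- record the VAS as not obtainable, with the reason, and try again within the same day's window, after reconciling 9AM-12PM in section 7.2.5 with 9AM-12AM in section 10.4;
- continue the scheduled VAS and surveys, blinded, on each later occasion when the patient is able;
- log the subject's deviations;
- in section 8.3, keep all randomised patients in their assigned group, state how a missing POD 1 score is handled with a sensitivity analysis, and bring section 8.2 into line with 3.3.2;
- report missed scores, deviations and removals by arm, with reasons.

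The investigators should reconcile 3.3.1, 3.3.2 and 19.6 on when clinical need requires stopping study treatment or unblinding. That is not a statistical decision.

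The cost is protocol wording and one reason code on the VAS form. The small downside is that some retained patients will have imperfect adherence, which the deviation log will show.
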